Current 'gold standard' testing when reactive hypoglycaemia is suspected is with an extended oral glucose tolerance test or mixed meal test. Where spontaneous hypoglycaemia is suspected and where facilities exist, the 'gold standard' test is an admission to Hospital for a 72 hour fast with twice daily laboratory measurements of plasma glucose, insulin and c-peptide. Finger prick glucose measurements are taken throughout the day to check for asymptomatic hypoglycaemia. Additional laboratory measurements are made if the patient becomes symptomatic. The prolonged fast is terminated when a diagnostic laboratory glucose measurement of $<2.2\text{mmol/L}$ is reached. Where a 72 hour fast is not possible, attempts are made to test insulin and glucose after three separate 15 hour fasts but this risks out of hospital hypoglycaemia and all its potential sequelae. These investigations attempt to mimic the situations which precipitate the hypoglycaemia but, in particular for reactive hypoglycaemia, often fail to do so.

Pathophysiology and significance of hypoglycaemia

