6.3 Primary endpoint

Arm 1 -

Outpatient - CGM findings reflect patient's fingerprick glucose readings

- Episodes of true hypoglycaemia (as decided by finger prick glucose testing) are captured by the CGM device

- CGM detects hypoglycaemia whilst patient is asleep

Inpatient - 72 hour fast - CGM device calls hypoglycaemia when fingerprick/lab glucoses also do

Arm 2 -

Blinded phase - CGM findings reflect patient's fingerprick glucose readings - any episodes of true hypoglycaemia (as decided by fingerprick glucose testing) are captured by CGM device

unblinded phase - CGM recordings help with titration of anti hypoglycaemic medications and this reduces overall incidence of hypoglycaemic episodes or duration of time spent in hypoglycaemic range

For patients experiencing asymptomatic hypoglycaemic episodes, a reduction in asymptomatic hypoglycaemic episodes and regaining of hypoglycaemic symptoms.

For patients with symptomatic hypoglycaemia, a reduction in symptomatic episodes.

7. Study population

Clinicians in the endocrinology department at St Bartholomew's hospital will be notified of this study and encouraged to refer forward suitable patients from their clinics.

Arm 1

Patients referred to the endocrinology department at St Bartholomew's hospital for investigation of suspected hypoglycaemia by either GPs or other clinical teams in the same or external NHS trusts will be referred onwards to the study team by the doctor that sees them for their routine clinical care.

Arm 2

Patients known to the endocrinology department at St Bartholomew's hospital with hypoglycaemia that are medically managed or who are to start medical management will be referred to the study team by the doctor that sees them for their routine clinical care.

Some patients who are found to have hypoglycaemia through arm 1 of this study will be automatically offered the chance to partake in arm 2 if they are to have medical treatment.

No vulnerable groups will be included – all patient will be able to give valid consent on their own behalf
All patients will be able to understand sufficient English to give informed consent on their own behalf.

Inclusion Criteria

Able and willing to give informed consent. No vulnerable adults will be included.
Either conventional gender, or non-binary.
Age >18 years
Any ethnicity
Any socio economic group
Medical condition as detailed above – arm 1 under investigation for possible/probable hypoglycaemia

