Arm 2 – on medical therapy for established hypoglycaemia

Exclusion criteria

Unwilling or unable to give consent
Unable to speak sufficient English to give consent and understand study requirements
Age<18
Lack of capacity to consent
Underlying hepatic condition
Current excessive alcohol consumption (men regularly consuming >50 units/week, women >35 units/week)
Diabetes Mellitus
Current use of Diabetic medication or insulin
Currently pregnant
Any patient on haemo or peritoneal dialysis

Length of study participation

Arm 1 - investigation of hypoglycaemia - maximum of 10 days of monitoring (5 days as an outpatient, max 5 days as an inpatient).
Arm 2 - evaluating anti hypoglycaemic drugs - maximum of 10 days of initial monitoring (investigator and patient blinded to CGM results), then up to a maximum of a further 20 days (unblinded) monitoring, likely to be far less than this though.

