Patients who have been diagnosed with spontaneous hypoglycaemia which requires medical therapy will be given a CGM kit and a finger prick glucose monitoring device and glucose monitoring diary. Patients will take the standard medical therapy and perform finger prick glucose testing when they experience symptoms that they attribute to hypoglycaemia. These values will be recorded in the glucose monitoring diary. After (up to) 10 days of blinded CGM monitoring, the diary and CGM data will be reviewed. A member of the endocrine team (consultant or registrar with consultant approval) will then make changes to the medical therapy in order to abolish any remaining episodes of hypoglycaemia. Patients will then wear the CGM device in unblinded mode for up to a further 20 days (though likely to be far less) in order to facilitate further medication titrations. Patients will be asked to confirm low CGM glucose readings during this time with a finger prick glucose measurement.

The study organisers will observe the glucose data obtained from the CGM and match it with finger prick glucose readings (from glucose monitoring diaries) and lab glucose data to check for concordance.

CGM data (in conjunction with glucose monitoring diaries) will be scrutinised and compared against drug regimens to see which doses needed to be altered, or where additional medication is required.

Patients will complete a modified Clarke and Gold hypoglycaemia questionnaire at the start of arm 2. They will complete an adapted questionnaire prior to surgery for their hypoglycaemia (if indicated) or at 6 months after the start of arm 2 – whichever comes first.

9. Study procedures

Arm 1

Patients will be recruited either through attendance at endocrinology outpatients at St Bartholomew's hospital or through inpatient transfer to St Bartholomew's hospital – both with suspected diagnoses of hypoglycaemia.

If attending the outpatients department with suspected hypoglycaemia and thought to be suitable for the study, then the patient will meet a member of the study team after their outpatient appointment or they will be offered an appointment to discuss the study at a mutually convenient time. Informed consent will be obtained during this meeting.

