12.2 Method of analysis

P<0.05 will be considered statistically significant

Arm 1

Positive and negative predictive value of CGM diagnosis of hypoglycaemia as an outpatient or an inpatient vs 72 hour fast (considered the 'gold standard')

Arm 2

In each patient, comparison of number of episodes of hypoglycaemia by finger prick glucose vs CGM vs symptoms during CGM blinded phase.

Severity of hypoglycaemia excursions

Amount of time spent in the hypoglycaemic range after medication titration – as measured by area under the curve on a time vs glucose graph generated by CGM machine. Comparisons of mean hypoglycaemic frequency and time within hypoglycaemic range within patients (blinded vs unblinded phase) using paired T test.

Change in hypoglycaemia questionnaire score before/after CGMs monitoring and medication titration

Regain of symptomatic hypoglycaemia in patients with asymptomatic hypoglycaemia, reduction of symptomatic hypoglycaemia in other patients.

13. Ethics

- Informed consent

Patients will be offered the chance to partake in the study should their treating consultant feel that they meet the inclusion criteria. Declining an invitation to take part in the study or leaving at any time means that the patient will default back to standard of care investigations. Their care will not be prejudiced or compromised in any way through either taking part or not taking part in the study.

- Recruitment

Only patients under investigation/treatment for hypoglycaemia at St Bartholomew's hospital will be considered for entry to the study. Patient being treated/investigated elsewhere who wish to be considered for the study would need to have their care transferred to St Bartholomew's by their GP/current endocrinologist.

- Inclusion / exclusion criteria

Inclusion/exclusion criteria is intended to screen out patients who have conditions that may affect their blood glucose (Diabetes Mellitus, underlying hepatic pathology) or in whom CGM is not recommended (pregnancy, critical illness) or in whom hypoglycaemia may be caused by extrinsic factors such as Diabetes medication.

- Study design

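### The arm 1 outpatient primary endpoint in 6.3 (CGM capture of finger-prick-confirmed lows) is not estimated by the only arm 1 analysis in 12.2, which is PPV/NPV against the 72-hour fast

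*Protocol*

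**What the plan says.** Protocol section 6.3 lists, for arm 1 outpatients, "Episodes of true hypoglycaemia (as decided by finger prick glucose testing) are captured by the CGM device". It also lists general agreement with finger-prick readings and detection during sleep. For the inpatient 72-hour fast the endpoint is "CGM device calls hypoglycaemia when fingerprick/lab glucoses also do".

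Section 12.2 gives one line of analysis for arm 1: "Positive and negative predictive value of CGM diagnosis of hypoglycaemia as an outpatient or an inpatient vs 72 hour fast", with the fast named as the gold standard. For arm 2, by contrast, 12.2 includes a "comparison of number of episodes of hypoglycaemia by finger prick glucose vs CGM vs symptoms during CGM blinded phase".

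Two other places bear on the comparison. Section 8 says the organisers will take the CGM data and "match it with finger prick glucose readings (from glucose monitoring diaries) and lab glucose data to check for concordance". Section 17.1 says the pre-admission finger pricks in arm 1 are there as a correlate for the CGM data. Neither names a statistic, and 12.2 takes up neither for arm 1.

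On the fast itself, section 5 states: "The prolonged fast is terminated when a diagnostic laboratory glucose measurement of" less than 2.2 mmol/L is reached. It adds that the standard investigations try to reproduce the circumstances that bring on hypoglycaemia but, "in particular for reactive hypoglycaemia, often fail to do so".

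**The concern.** An analysis of a primary endpoint should use that endpoint's unit and reference. Here both change between 6.3 and 12.2. The endpoint asks whether CGM read low when a finger prick showed a low. The analysis asks whether a CGM diagnosis agrees with the outcome of an admission test that comes after the outpatient days.

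If 12.2 is followed as written, the arm 1 report will contain no capture figure for the outpatient days. Readers may then take the predictive values as evidence on capture, which they are not. The secondary objective (6.2), whether CGM records hypoglycaemia accurately, would also lack an arm 1 answer from the outpatient period.

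**Working it through.** The plan has no figure to reproduce: the 30 patients in 12.1 come with no derivation, and no arm 1 number is given. The check is a comparison of the text, followed by an illustration.

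**Step 1. Endpoint against analysis.**

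| | 6.3 outpatient | 6.3 inpatient | 12.2 arm 1 |
|---|---|---|---|
| Unit | episode | CGM call at the time of a reading | diagnosis (per patient is implied, not written) |
| Reference | finger prick | finger prick or lab glucose | outcome of the 72-hour fast |
| Timing | same time | same time | for outpatient CGM, a later test; CGM starts 5 days before admission (section 8) |

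**Step 2. Direction of the distortion.** Take two outpatients, each with four finger-prick-confirmed lows and a negative fast.
- CGM misses all four and shows no other low. Under 6.3 this is 0 of 4 captured; under 12.2 it is a true negative.
- The lows are reactive and CGM catches all four. Under 6.3 this is 4 of 4 captured; under 12.2 it is a false positive. If 5 of 15 CGM-positive patients were like this and the other 10 had a positive fast, PPV would be 10/15 = 66.7%, although CGM was right in all 15.

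**Step 3. How far missed episodes could be hidden.** Let s be the capture probability per episode, k the number of independent episodes per patient, p the prevalence and sp the patient-level specificity. The protocol gives none of these, so all are assumptions. It is also assumed that the patients with true episodes are those with a positive fast.

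- Patient-level sensitivity: S = 1 − (1 − s)^k
- PPV = pS / [pS + (1 − p)(1 − sp)]
- NPV = (1 − p)sp / [(1 − p)sp + p(1 − S)]

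With s = 0.5, k = 5, p = 0.5, sp = 1:
- S = 1 − 0.5^5 = 0.969
- PPV = 100%
- NPV = 0.5 / (0.5 + 0.5 × 0.03125) = 97.0%, with half the episodes missed

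Varying k with the rest unchanged (PPV stays at 100%):

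| k | S | NPV |
|---|---|---|
| 1 | 50.0% | 66.7% |
| 2 | 75.0% | 80.0% |
| 3 | 87.5% | 88.9% |
| 5 | 96.9% | 97.0% |

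Other inputs:
- At k = 5 and s = 0.5, NPV runs from 98.7% (p = 0.3) to 93.2% (p = 0.7).
- With sp = 0.9 and p = 0.5, PPV is 90.6% and NPV 96.6%.
- At k = 1 and sp = 1, NPV runs from 82.4% (p = 0.3) to 46.2% (p = 0.7), so nothing is masked.
- If misses within a patient were perfectly correlated (all caught or all missed), S would equal s = 0.5 whatever k is, and NPV at p = 0.5 would be 66.7% again.

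**Step 4. Inpatient period.** The fast's diagnostic criterion is itself a lab glucose, so its reference overlaps with the one in 6.3. The fast stops when that value is reached, which leaves about one diagnostic episode per patient. This is close to the k = 1 row.

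**The case against.** The strongest reply is that PPV/NPV against the fast is a proper analysis. Objective 1 in section 6.1 and the rationale in 5.4 ask whether CGM can exclude hypoglycaemia and spare an admission. That is a question about diagnosis, and NPV against the fast addresses it. This stands: the predictive values are not an error and should not be dropped.

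A second reply is that matching of CGM with finger pricks is planned in sections 8 and 17.1, and that a window and a statistic can be left to an analysis plan. This stands in part: the data will exist. But 12.2 is not silent on arm 1. It names an analysis, and that analysis estimates something other than the outpatient endpoint. It does name an episode comparison for arm 2.

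A reader might infer more: that the same data would show 50–60% capture under 6.3 and 88–99% under 12.2, so the plan is bound to make CGM look near-perfect. The documents do not support this. The 88–99% is patient-level sensitivity (s of 0.5 or 0.6, k of 3 or 5), which 12.2 does not report. It rests on assumed values and on independent misses, and sensor error shared across one patient's episodes would shrink it. It also gives one direction only, whereas the protocol's own remark on reactive hypoglycaemia shows that the fast can penalise CGM.

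**Conclusion.** The point holds for the arm 1 outpatient endpoint. The arm 1 analysis in 12.2 leaves out the outpatient finger pricks that define truth in 6.3, so capture is not estimated. This follows from the text and needs no assumption beyond reading a diagnosis against one fast as one result per patient.

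The size and direction of any distortion are unknown. The illustration (NPV about 97%, PPV 100%, half the episodes missed) shows what is possible with several independent episodes per patient and high specificity. It is not a forecast. For the inpatient endpoint the mismatch is smaller.

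**What to change.** Add to 12.2, as the arm 1 analysis of the 6.3 endpoint:

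- The proportion of finger-prick- or lab-confirmed lows captured by the CGM reading nearest in time, with the matching window and the definition of a low fixed before the data are seen.
- Separate results for the outpatient and inpatient periods.
- A 95% confidence interval that allows for several episodes per patient, read with caution because patients are few (30 over both arms).
- The number of CGM lows not confirmed by a paired reference value. Outpatient finger pricks are prompted by symptoms, so CGM lows with no paired reading should be counted apart from those that a paired reading contradicts.

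Keep patient-level PPV/NPV against the fast alongside, labelled as the analysis for objective 1, and write the unit into the text. A cross-reference from 12.2 to the matching in section 8 would join the two.

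The cost is a little more analysis on diary, meter, lab and CGM data that are already collected. The headline figure may be less favourable.

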6.1 Primary objective

- 1) Use CGM (blinded to the patient and investigator) in advance of standard investigations (where possible) in order to record whether patient symptoms correlate with recorded hypoglycaemia. This may exclude hypoglycaemia as a cause of symptoms and allow the patient to avoid a prolonged inpatient investigation.
- 2) Use CGM technology (blinded to the patient and investigator) alongside standard investigations for patients with both reactive and spontaneous hypoglycaemia to evaluate the relative efficacy of the two methods in detecting hypoglycaemia episodes.
- 3) Use CGM (blinded to the patient and investigator) to record frequency of hypoglycaemia after medical treatment has been initiated in order to assess its

effectiveness in detecting hypoglycaemic episodes of which the patient may not have been aware, potentially reducing the need for painful fingerprick glucose testing.

4) Use CGM (unblinded) to titrate medication to abolish hypoglycaemia in order to improve outpatient management and improve patient safety. The Dexcom system has an alarm to alert patients to hypoglycaemia which will be used in the unblinded phase.

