17.3 Tools

Each patient will receive a glucose monitoring diary where they can record the finger prick glucose level, time, date and symptoms.

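### For the arm 2 blinded phase, Protocol section 12.2 compares episode totals and leaves out the matched analysis that the primary endpoint and section 8 call for

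*Protocol*

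**What the plan says.** Four places in the Protocol bear on this point.

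- **Endpoint.** Section 6.3, arm 2 blinded phase, asks that "any episodes of true hypoglycaemia (as decided by fingerprick glucose testing) are captured by CGM device". The unit is the single confirmed episode.
- **Analysis.** Section 12.2, arm 2, answers with "In each patient, comparison of number of episodes of hypoglycaemia by finger prick glucose vs CGM vs symptoms during CGM blinded phase". The unit is the patient's total. The other arm 2 lines in 12.2 concern severity, time in the low range, the blinded versus unblinded comparison, the questionnaire and the return of symptoms. None of them addresses capture in the blinded phase.
- **Design.** Section 8 asks arm 2 patients to "perform finger prick glucose testing when they experience symptoms that they attribute to hypoglycaemia". It also says that the study team will take the CGM data and "match it with finger prick glucose readings (from glucose monitoring diaries) and lab glucose data to check for concordance". It attaches no statistic to that matching.
- **Data.** Under section 17.3 the diary lets patients "record the finger prick glucose level, time, date and symptoms", so finger pricks can be placed in time against the CGM trace.

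Objective 3 in section 6.1 adds a separate aim for the same phase: to record how often lows occur and to assess the CGM's "effectiveness in detecting hypoglycaemic episodes of which the patient may not have been aware".

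**The concern.** Whether a confirmed low was captured is a question about pairs: did CGM read low at the time of this finger prick? A comparison of totals discards the pairing. Two methods can report the same number of episodes without having found the same ones, and they can report different numbers although every confirmed low was found by both.

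Both cases are plausible here. In the blinded phase, patients are asked to test when they feel symptoms, while CGM runs continuously for up to 10 days and is meant to pick up lows that the patient does not notice. CGM episodes with no finger prick beside them are therefore expected, and they enter the CGM total alongside any spurious ones. If 12.2 is followed as written, a primary endpoint of this phase is reported through a figure that does not measure it, although the matching that would measure it is promised elsewhere in the same document.

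**Working it through.** The Protocol states no capture rate, episode rate or power figure for this comparison, so there is no planned figure to reproduce. The check is algebra followed by examples. All episode numbers below are assumptions.

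**Notation, for one patient.** F = finger-prick-confirmed lows; C = CGM episodes; m = confirmed lows that CGM also called; u = CGM episodes with no matching finger prick.

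- C = m + u, and missed lows = F − m.
- Quantity in 12.2: C − F = u − (F − m), that is, unmatched CGM episodes minus missed lows.
- Quantity in 6.3: capture = m/F.

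The count difference is zero whenever u equals the number missed, whatever m is.

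**Equal totals (assumed F = C = 10).**

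| m | missed | u | C − F | capture |
|---|---|---|---|---|
| 10 | 0 | 0 | 0 | 100% |
| 8 | 2 | 2 | 0 | 80% |
| 5 | 5 | 5 | 0 | 50% |
| 2 | 8 | 8 | 0 | 20% |
| 0 | 10 | 10 | 0 | 0% |

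**The offset need not be spurious.** Assume 10 true lows, 6 of them symptomatic and tested, and a CGM that detects 60% of lows of either kind. Expected matched lows are 0.6 × 6 = 3.6, and expected silent lows found are 0.6 × 4 = 2.4. The CGM total is 3.6 + 2.4 = 6 against 6 finger-prick lows, yet capture is 3.6/6 = 60% with no false CGM reading. A CGM that finds everything gives 10 against 6, with capture 6/6 = 100%.

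**Unequal totals with full capture.** Assume 20 true lows, all seen by CGM, with 50% symptomatic and tested. The totals are 20 and 10, a difference of 10, and capture is 10/10 = 100%.

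**Across patients.** Assume F ~ Poisson(5) per patient, capture probability s, and unmatched CGM episodes ~ Poisson(5(1 − s)). The mean CGM count is 5s + 5(1 − s) = 5, equal to the mean of F. Over 10,000 simulated trials for each setting, a paired t-test on C − F at two-sided 0.05 rejected in 4.2% to 5.3% of runs. This held for n = 10, 15 and 30 and for s = 0.9, 0.7 and 0.5. That is about the nominal error rate, so under an equal offset the totals carry no information on capture. The Protocol names no test for this line; the t-test only illustrates what a formal comparison of totals could see.

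**Without an offset.** If u = 0, then C − F = −(F − m), and missed lows do show as a lower CGM total. The totals mislead to the extent that unmatched CGM episodes occur.

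**The case against.** The strongest reply is that the matching is already planned. Section 8 commits the team to match CGM with finger-prick and laboratory readings, and the diary holds the times. A reader of 12.2 alone might infer that the trial never examines whether the same episodes were found. The Protocol as a whole does not support that. What stands is narrower: the section that fixes the analysis does not take up the matching, and section 8 gives it no summary measure.

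Second, 12.2 nowhere says that equal totals mean agreement. It names a comparison without a conclusion or a test, and the paired t-test there belongs to the blinded versus unblinded contrast. It would be wrong to say that the plan will declare CGM accurate on equal totals.

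Third, the totals suit objective 3. More CGM episodes than symptoms is what a device that finds unnoticed lows should show, and capture of finger-prick lows cannot describe episodes that nobody tested. This stands, and the totals should be kept.

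Fourth, a reader might infer from section 8 that the finger-prick total can never exceed the symptom total. The text asks for testing at symptoms but does not exclude other tests. Section 5.4 mentions regular daytime checks for patients without awareness, and section 17.1 calls finger-prick testing standard in home monitoring of treated patients.

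Finally, the time window and the form of the interval are details that an analysis plan may hold, and this is a 30-patient pilot. Their absence is not the point. The point is that 12.2 states a quantity different from the endpoint, and sample size does not change that.

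**Conclusion.** The point holds in a limited form. Section 12.2 assigns to the arm 2 blinded phase a comparison of totals that does not estimate the capture endpoint in section 6.3, and it leaves out the matching promised in section 8. Logically the gap can be complete: equal totals are compatible with capture from 0% to 100%. Its size in this trial is unknown. The examples rest on assumed rates and on offsets chosen to be equal, so they show what is possible, not what is likely. A reader might infer that many confirmed lows will in fact be hidden; the documents give no figure to support that. Because timed readings are collected and matching is intended, nothing is lost beyond recovery. This should be fixed before analysis, but it does not undermine the study.

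**What to change.** In section 12.2, make the matched analysis the stated analysis for the arm 2 blinded-phase endpoint:

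1. Pair each diary finger prick with the CGM reading nearest in time, inside a window set before the data are seen (15 minutes, for example). Section 5 describes quarter-hourly readings, so with no data loss the nearest reading is at most 15/2 = 7.5 minutes away.
2. Cross-classify the pairs as low or not low on each method. Report the proportion of finger-prick lows at which CGM was low, and the proportion of non-low finger pricks at which CGM was also not low.
3. Give confidence intervals that treat the patient as the cluster, because one patient contributes several pairs.
4. List CGM lows with no finger prick separately as unverified, counting them neither as extra detections nor as errors.
5. Keep the three-way totals as the descriptive analysis for objective 3.

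The cost is one paragraph in 12.2 and a little more analysis work. No new data, visits or tests are needed.
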